**IRBs/IECs**

A copy of this amended protocol will be sent to the Institutional Review Board (IRBs)/Independent Ethics Committee (IECs) and Health Authorities.

The changes described in this amended protocol are substantial and require IRB/IEC approval prior to implementation.

The changes herein affect the Informed Consent. Sites are required to update and submit for approval a revised Informed Consent that takes into account the changes described in this protocol amendment.

## Protocol summary

Protocol number	CAMG334A2304
Full Title	A 12-week phase 3, randomized, double-blind, placebo-controlled study to evaluate the efficacy and safety of once monthly subcutaneous erenumab 70 mg in adult chronic migraine patients
Brief title	Study of efficacy and safety of erenumab in adult subjects with chronic migraine
Sponsor and Clinical Phase	Novartis Phase III
Investigation type	Biological
Study type	Interventional
Purpose and rationale	The purpose of this study is to obtain data from regions not adequately represented in the global chronic migraine (CM) pivotal Study 2012095, and to support registration of 70 mg erenumab in China. It has a similar design to the global pivotal study.
Primary Objective(s)	The primary objective of this study is to evaluate the effect of erenumab compared to placebo by measuring the change in monthly migraine days (MMD) from baseline to the last 4 weeks of the 12-week treatment period.
Secondary Objectives	Objective 1: To evaluate the effect of erenumab compared to placebo on change in migraine-related disability and productivity as measured by the modified Migraine Disability Assessment (mMIDAS) from baseline to the last 4 weeks of the 12-week treatment period  Objective 2: To evaluate the effect of erenumab compared to placebo on the proportion of subjects with at least 50% reduction in monthly migraine days from baseline to the last 4 weeks of the 12-week treatment period  Objective 3: To evaluate the effect of erenumab compared to placebo on the change in monthly acute headache medication days from baseline to the last 4 weeks of the 12-week treatment period  Objective 4: To evaluate the safety and tolerability of erenumab, including adverse events (AEs), clinical laboratory values, vital signs, and anti-AMG 334 antibodies
Study design	This study uses a single-cohort, 2-treatment arms, randomized (1:1 (70 mg: placebo)), double-blind study design in adult subjects with chronic migraine. A screening period of 2 weeks will be used to assess initial eligibility, followed by a 4-week baseline period to assess diary compliance and headache frequency. Eligible patients will then be randomized to either erenumab 70 mg or placebo for 12 weeks, followed by an open-label treatment period to last until launch of erenumab in the country or until June 2021 in Korea. A safety follow-up visit will occur 12 weeks after the last treatment for subjects who discontinue the double-blind treatment or who complete the double-blind treatment period without continuing in the open-label treatment period.  An unblinded interim analysis (IA) will be conducted after 70% (385) of subjects have completed the double-blind treatment period (including early withdrawals), to determine whether the study will stop early or continue to the final primary analysis (full sample size). The recruitment continues until the read-out of the unblinded interim analysis.

Study Population	The study population will consist of male and female subjects, ages 18 to 65, with a documented history of chronic migraine as outlined in the inclusion criteria. Approximately 550 subjects will be randomized in China and other Asian countries/regions (approximately 350 Chinese subjects for final analysis or around 250 for the unblinded interim analysis). Assuming a 30% screening failure rate, approximately 790 subjects are anticipated to be screened.
Key Inclusion criteria	
 
• Adults <math>\geq</math> 18 to <math>\leq</math> 65 years of age upon entry into screening
 
• History of at least 5 attacks of migraine (with or without aura) based on medical records and/or patient self-report
 
• History of <math>\geq</math> 15 headache days per month of which <math>\geq</math> 8 headache days were assessed by the subject as migraine days per month in each of the 3 months prior to screening
 
• <math>\geq</math> 15 headache days of which <math>\geq</math> 8 headache days meet criteria as migraine days during the baseline period based on the electronic Diary (eDiary) calculation (Refer to Section 8.3.1 for definition of migraine day)
 
• Demonstrated at least 80% compliance with the eDiary during the baseline period based on the eDiary calculation
 
• History of migraine (with or without aura) for <math>\geq</math> 12 months prior to screening according to the IHS Classification based on medical records and/or patient self-report
 

Key Exclusion criteria	
 
• Older than 50 years of age at migraine onset
 
• Taken an opioid and/or opioid-containing analgesic for any indication during more than 4 days within one month prior to the start of the baseline period or during the baseline period
 
• Taken a butalbital-containing analgesic for any indication during more than 2 days within one month prior to the start of the baseline period or during the baseline period
 
• Prior migraine prophylaxis treatments failure in more than 3 out of the following medication categories: 
 
• Category 1: Divalproex sodium, sodium valproate
 
• Category 2: Topiramate
 
• Category 3: Beta blockers (for example: atenolol, bisoprolol, metoprolol, nadolol, nebivolol, pindolol, propranolol, timolol)
 
• Category 4: Tricyclic antidepressants (for example: amitriptyline, nortriptyline, protriptyline)
 
• Category 5: Flunarizine, verapamil, cinnarizine
 
• Category 6: Serotonin-norepinephrine reuptake inhibitors (for example: venlafaxine, desvenlafaxine, duloxetine, milnacipran)
 
• Category 7: Botulinum toxin
 
• Category 8: lisinopril, candesartan
 
• Category 9: Pregabalin, gabapentin
 
• Category 10: Zonisamide
 
• Category 11: Memantine
 
• Category 12: Pizotifen
 
 
 
• Use of a prohibited medication for migraine prophylaxis within 5 half-lives, or a device or procedure for migraine prophylaxis within one month prior to the start of the baseline period or throughout the study (Refer to Section 6.2.2 for the list of these excluded therapies)
 

	

Prior Botulinum toxin A treatment in the head/neck region within 4 months prior to the start of the baseline period or during the baseline period

Study treatment	
In the double-blind treatment period:
 

Erenumab 70 mg/1 mL pre-filled syringe

Matching placebo in 1 mL pre-filled syringe, identical in appearance

 
In the open-label treatment period:
 

Erenumab 70 mg/1 mL pre-filled syringe

Efficacy assessments	Migraine days
Key safety assessments	

Adverse event monitoring

Physical examination

Vital signs

Laboratory evaluations, including anti-AMG 334 antibody testing

Electrocardiogram (ECG)

Other assessments	

Patient reported outcomes (PROs)

Modified Migraine Disability Assessment Questionnaire (mMIDAS)

Beck Depression Inventory-II (BDI-II)

Clinical Outcome Assessments (COAs): eDiary

Data analysis	
The primary efficacy endpoint variable will be analyzed using a generalized linear mixed model based on observed monthly data during the treatment period.
 
The secondary efficacy endpoints will be analyzed using a linear mixed effects model similar to the primary endpoint. The dichotomous endpoints will be analyzed by Cochran-Mantel-Haenszel (CMH) test with subjects who are missing monthly migraine day data during the last 4 weeks of treatment period imputed as non-responders. Nominal 95% confidence intervals and p-values will be reported. Tests of secondary endpoints will be tested at nominal 2-sided significant level 0.05.

Key words	AMG 334, erenumab, migraine, chronic, headache, Chinese

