### **6.3.2 Treatment assignment, randomization**

At Day 1, all eligible subjects will be randomized via Interactive Response Technology (IRT) to one of the treatment arms. The investigator or his/her delegate will contact the IRT after confirming that the subject fulfills all the inclusion/exclusion criteria. The IRT will assign a randomization number to the subject, which will be used to link the subject to a treatment arm and will specify a unique medication number for the first package of study drug to be dispensed to the subject. The randomization number will not be communicated to the caller.

The randomization numbers will be generated using the following procedure to ensure that treatment assignment is unbiased and concealed from subjects and investigator staff. A subject randomization list will be produced by the IRT provider using a validated system that automates the random assignment of subject numbers to randomization numbers. These randomization numbers are linked to the different treatment arms, which in turn are linked to medication numbers. A separate medication list will be produced by or under the responsibility of Novartis Global Clinical Supplies using a validated system that automates the random assignment of medication numbers to packs containing the investigational drug(s).

Randomization will be stratified by prior prophylactic migraine treatment failure (Yes vs. No) and presence of medication overuse (Yes vs. No) during baseline according to the planned randomization ratio within each stratum. The randomization scheme for subjects will be reviewed and approved by a member of the Randomization Group.

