### 8.3.2 Appropriateness of efficacy assessments

Monthly migraine days (MMD) is a clinically relevant and commonly accepted primary endpoint in accordance with current standards and guidelines (Tassorelli et al 2018, Tfelt-Hansen et al 2012) for migraine prophylactic studies. The definition of migraine day (Section 8.3.1) in this study is adapted based on the diagnostic criteria of ICHD-3 (3rd edition 2018) and the clinical practice in China. Acute migraine-specific medication (mainly triptan) use is very common in global countries or regions. In global pivotal Study 20120295 in CM population, 75%-79% patients used acute migraine-specific medication during baseline. However, the use of triptan or ergots is extremely low in China (Jiang et al 2016). Almost all of migraine patients in China usually use migraine unspecific analgesics such as NSAIDs or combination analgesics for the acute treatment of migraine. Due to the difference in use pattern of acute migraine-specific medication (mainly triptans) between Chinese and the global migraine population, the criteria of migraine day in ICHD-3 makes this clinical tool less applicable in our clinical setting, and argues for inclusion of other acute migraine-unspecific medications in the definition of migraine day in this study to better illustrate Chinese patients characteristics. This definition of migraine day was also aligned with China CDE. The monthly migraine days will be calculated using migraine day data collected from the eDiary.

As the mean change in MMD however describes a population-based measure and given the natural variability in migraine trials often is associated with small effect sizes, clinically an important complementary information is the proportion of patients that achieve a certain clinically meaningful response, which is usually described with achieving at least a 50% reduction of migraine days compared to the individual baseline (“50% responder rate”). In pivotal trials, 50% (or higher) responder rates are usually included as secondary or key secondary outcomes.

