### **12.4.2 Statistical model, hypothesis, and method of analysis**

The null hypothesis is that there is no difference in the change from baseline in monthly migraine days in the last 4 weeks of the 12-week treatment period between erenumab group and placebo group versus the alternative hypothesis that there is a difference between the two groups. The null hypothesis will be rejected if the observed p-value for the between-group comparison is less than the significant level adjusted according to the alpha spending function with the O'Brien-Flemming approach. The nominal p-value threshold will be calculated upon the exact information collected in the interim analysis, considering the alpha-level spent at interim analysis and considering the actual correlation among the test statistics, in order to achieve a cumulative type I error smaller than the desired significance level (i.e. smaller than the 5% for a two-sided test). The primary efficacy endpoint variable will be analyzed using a generalized

linear mixed model with treatment, scheduled visit, treatment by visit interaction, and the stratification variables and baseline values as covariates. If applicable, unstructured covariance structure is assumed. Least squares means (LSMs) for treatment groups and its associated 95% confidence intervals, difference of LSMs compared to placebo group and the associated 95% confidence interval of the difference, as well as the nominal two-sided p-values, will be tabulated by visit and treatment.

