## 12.8 Sample size calculation

### 12.8.1 Primary endpoint(s)

The planned total sample size in this proposed China-centric phase 3 study is 550 subjects. The key assumptions in calculating the sample size are based on prior results from erenumab global pivotal study. A treatment difference in terms of change from baseline on MMDs during Week 9-12 (primary endpoint) for erenumab 70 mg vs. placebo is assumed at -2.0 days. The common standard deviation of the primary variable is assumed at 6.8. Given a 1:1 randomization ratio among erenumab 70 mg and placebo, it requires a total of 550 subjects (including 10% drop out rate) to achieve approximate 90% power to demonstrate the treatment difference of erenumab 70 mg compared with placebo under two-sided 0.05 alpha level. The impact of spending alpha at unblinded interim analysis on sample size and power is relatively negligible. Having this interim analysis with alpha spending at 0.014 two-sided, at final analysis an observed p-value

$\leq 0.046$  two-sided would be required (given that the interim analysis was performed when 70% subject finished treatment or early withdraw). With that said, the overall power will be maintained approximately at 90% with planned sample size.

The sample size for Chinese sub-population will make sure the consistency of treatment effect between Chinese and total population. The methods for consistency assessment is proposed as,

$$\Pr(D_{\text{China}} / D_{\text{Overall}} > 0.5) > 95\%,$$

which means that this China study should have high probability ( $>95\%$ ) to demonstrate consistency where the treatment effect (treatment difference of erenumab compared with placebo) observed in the Chinese population should be as high as at least 50% of the treatment effect observed in the overall study population in the prospective trial, assuming there is no difference between the Chinese population assessed in the trial and the overall population.

To meet the above criteria, approximately 350 (out of 550 for the overall study) Chinese subjects will be recruited.

At the interim analysis, as long as China population takes the majority of the overall population, there should have high likelihood to demonstrate the consistency as well.

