2.2.1 Subgroup of interest

The primary and secondary efficacy endpoints, safety endpoints (adverse events, clinical laboratory values, vital signs, and anti-AMG 334 antibodies), as well as the demographics and baseline characteristics, and the prior migraine prophylactic medication usage information will be analyzed for Chinese subgroup (recruited from China mainland and 3 qualified sites from Taiwan). This is to evaluate the consistency of efficacy and safety effects in Chinese population vs overall population.

In addition, the effect in the following subgroup analysis by baseline characteristic will be investigated with respect to the primary and secondary efficacy analyses as well:

- Prior prophylactic migraine medication treatment failure (Yes or No)
- Medication overuse at Baseline: Yes, No

- Baseline MMD (< median vs \geq median)
- Disease duration (< median vs \geq median)
- Age (< median vs \geq median)
- BMI (< median vs \geq median)
- Sex (Male vs Female)
- Region

The impact of other baseline variables, may be investigated with respect to the primary and secondary efficacy analyses if, upon clinical review, differences between treatment groups are deemed clinically meaningful.

The purpose of the subgroup analyses is to explore if the treatment effect varies across subgroups of interest. Subgroup analyses are performed for primary and secondary efficacy endpoints using the same method as primary analysis method but performed within each subgroup of interest. The treatment difference (or odds ratio) with associated 95% confidence intervals and p-values will be reported within each subgroup.

Note: if the subgroup is the stratification factor (Prior prophylactic migraine medication treatment failure) then it will not be included in the model.

The heterogeneity of the treatment effect across the subgroups will be evaluated for the primary and secondary endpoints by examining the treatment by subgroup interaction and the p-value for the interaction term will be reported. For continuous endpoints, the primary analysis model with the addition of subgroup and treatment group by subgroup interaction as two additional effects will be used. For endpoint based on proportions, a logistic regression model that includes treatment group, stratification factors, baseline value, subgroup and treatment group by subgroup interaction will be used.

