2.5.2 Statistical hypothesis, model, and method of analysis

The primary endpoint of the study will be tested for erenumab 70 mg compared to placebo.

Null hypothesis: There is no difference between erenumab 70 mg group and placebo group, in terms of change from baseline in monthly migraine days in the last 4 weeks of the 12-week treatment period.

Alternative hypothesis: There is a difference between erenumab 70 mg group and placebo group, in terms of change from baseline in monthly migraine days in the last 4 weeks of the 12-week treatment period.

The null hypothesis will be rejected if the observed p-value for the between-group comparison is less than the significant level adjusted according to the alpha spending function with the

O'Brien-Flemming approach. The nominal p-value threshold will be calculated upon the exact information collected in the interim analysis, considering the alpha-level spent at interim analysis and considering the actual correlation among the test statistics, in order to achieve a cumulative type I error smaller than the desired significance level (i.e. smaller than the 5% for a two-sided test).

The primary efficacy endpoint variable will be analyzed using a linear mixed effects repeated measures model based on observed monthly data during treatment period, with treatment, scheduled visit, treatment by visit interaction, and the stratification factors and baseline values as covariates. If applicable, unstructured covariance structure is assumed. Least squares means (LSMs) for treatment groups and its associated 95% confidence intervals, difference of LSMs compared to placebo group and the associated 95% confidence interval of the difference, as well as the nominal two-sided p-values, will be tabulated by visit and treatment.

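### Region is neither a randomisation stratum nor a primary-model term in this China-centric trial; pre-specifying a region term is a small, free gain in precision

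*Protocol*

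**What the plan says.** **Population.** The Protocol summary plans that "Approximately 550 subjects will be randomized in China and other Asian countries/regions". About 350 are to be Chinese, which leaves about 200 (550 − 350) from elsewhere in Asia. Protocol section 12 repeats the main analyses in Chinese patients. Protocol 12.8.1 and SAP section 3 size that group so that D_China/D_Overall exceeds 0.5 with probability above 95%.

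**Randomisation (Protocol 6.3.2).** "Randomization will be stratified by prior prophylactic migraine treatment failure (Yes vs. No) and presence of medication overuse (Yes vs. No) during baseline". No section adds region, country or site.

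**Primary model.** Protocol 12.4.2 specifies a generalized "linear mixed model with treatment, scheduled visit, treatment by visit interaction, and the stratification variables and baseline values as covariates". SAP 2.5.2 has the same terms: "with treatment, scheduled visit, treatment by visit interaction, and the stratification factors and baseline values as covariates". The Week 12 ANCOVA used after imputation (SAP 2.5.4) contains treatment, stratification factor and baseline only.

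**Where region does appear.** SAP 2.2.1 defines the Chinese subgroup as mainland China plus three qualified Taiwan sites. It also lists Region as a subgroup, without defining it. For continuous endpoints it fits the primary model plus a subgroup main effect and a treatment-by-subgroup interaction. A discretionary clause follows: "The impact of other baseline variables, may be investigated with respect to the primary and secondary efficacy analyses if, upon clinical review" the arms differ to a clinically meaningful degree.

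**The concern.** Region is the factor around which this trial is built. It defines the numerator of the consistency ratio, yet the denominator, D_Overall, which is also the primary estimate, is obtained without adjusting for it. If Chinese and other Asian patients differ in mean change whatever their treatment, two things follow. The between-region spread sits in the residual variance. And a chance difference between arms in the proportion of Chinese patients carries part of that regional difference into D_Overall.

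Timing matters too. If an imbalance became visible after unblinding and region were then added to the primary model, the adjustment would look data-driven. Naming the term in advance removes that argument.

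**Working it through.** **Inputs.** From Protocol 12.8.1: the difference "for erenumab 70 mg vs. placebo is assumed at -2.0 days"; "The common standard deviation of the primary variable is assumed at 6.8"; two-sided alpha 0.05; 1:1 allocation; 550 patients including 10% dropout, so 495 evaluable. Chinese share f = 350/550 = 0.636, so f(1−f) = 0.231. The regional difference in mean change, d, is **an assumption**: the documents give no figure, and 1 to 4 days is shown.

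**1. Reproduce the plan.** n per arm = 2 × (1.96 + 1.2816)² × 6.8² / 2.0² = 243, total 486, and 486/0.9 = 540 against the stated 550. With 495 evaluable, SE = 6.8 × √(4/495) = 0.611 and power = Φ(2.0/0.611 − 1.96) = 90.5%. With an O'Brien-Fleming-type interim look at 70% information, overall power is 90.1%. The Protocol's figure of about 90% reproduces.

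**2. Variance due to region.** Between-region variance is f(1−f)d², to be compared with 6.8² = 46.24. If 6.8 already contains this spread, adding region gives SE = 2 × √((46.24 − 0.231d²)/495).

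**3. Chance imbalance.** The SD of the between-arm difference in Chinese share is √(4f(1−f)/495) = 0.043, or 4.3 percentage points. Multiplied by d, it gives the 1-SD shift in D_Overall.

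| d (days) | f(1−f)d² | Share of 46.24 | Equivalent patients of 550 | 1-SD shift (days) | Power with region (90.5% without) |
|---|---|---|---|---|---|
| 1 | 0.23 | 0.5% | 3 | 0.04 | 90.7% |
| 2 | 0.93 | 2.0% | 11 | 0.09 | 91.1% |
| 3 | 2.08 | 4.5% | 25 | 0.13 | 91.7% |
| 4 | 3.70 | 8.0% | 44 | 0.17 | 92.7% |

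**4. The other reading of 6.8.** If 6.8 is the within-region SD, power is 90.5% with region in the model. Without it, power is 90.4%, 90.0%, 89.3% and 88.3% for d = 1 to 4.

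**5. Interim analysis.** With 250/385 Chinese and about 346 evaluable, the SD of the imbalance is 5.1 points. The 1-SD shift is 0.05 to 0.10 days for d = 1 to 2, against an SE of 0.73.

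**6. Validity.** We simulated 6,000 trials per setting (495 patients, randomisation not stratified by region, ordinary linear model rather than the repeated-measures model). With region omitted, type I error was 5.5%, 4.7% and 5.1% for d = 0, 2 and 4 (Monte Carlo error about 0.3 points). Mean estimates were −2.00, −1.98 and −1.99 for a true −2.0. At d = 4 the empirical SD of the estimate was about 0.64 without region and 0.61 to 0.62 with it.

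**7. Consistency.** D_China − 0.5 × D_Overall has mean −1.0 and variance Var(D_China) + 0.25 Var(D_Overall) − Var(D_Overall). The probability of meeting the criterion is 97.1% with 550 patients and 96.4% with 495, so the target of more than 95% is met at the final analysis without a region term. This assumes the same treatment effect in both groups, as the plan does.

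**The case against.** The strongest defence is that the plan adjusts for its randomisation factors plus baseline, which is a coherent choice, and that little is lost. Most of this stands.

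- **Bias.** A reader might infer that chance regional imbalance biases D_Overall. It does not. It is ordinary sampling error already covered by the standard error, and the simulation shows an unbiased estimate and type I error near 5%.
- **Adjustment route.** A reader might infer that the discretionary clause is the only way region can be adjusted for. It is not: the Region interaction model in SAP 2.2.1 already contains a region main effect. That model is exploratory, however, and leaves the primary estimate unchanged.
- **Evidence of a regional difference.** Protocol 8.3.2 might be read as showing one within the trial. Its contrast ("Due to the difference in use pattern of acute migraine-specific medication (mainly triptans) between Chinese and the global migraine population") is between Chinese and global patients, not Chinese and other Asian patients, and the migraine-day definition was widened in response to it.
- **Consistency.** A reader might take it to be judged between Chinese and other Asian patients. The criterion compares Chinese with overall. D_China is a within-China contrast, so imbalance in the Chinese share does not shift it.
- **Size of d.** The placebo group in the global chronic migraine study changed by 4.2 days in total (Protocol 1.1), so d = 4 is close to the whole placebo response and twice the assumed drug effect. Baseline migraine days and medication overuse, both in the model, may absorb part of any real difference.
- **Blinded re-estimation.** The pooled SD includes any between-region spread, and the sample size rises if it exceeds 6.8. This protects power, but with extra patients rather than a model term.

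What survives is that the factor is known for every patient, is central to the trial's purpose, and can be adjusted for at almost no cost if named in advance.

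**Conclusion.** The omission is real, and its effect is a small loss of precision. It is not a flaw in validity. For an assumed regional difference of 1 to 2 days, the gain from adding region is about 0.2 to 0.6 power points, worth roughly 3 to 11 patients. The larger gains in the table need differences of 3 to 4 days, for which the documents offer no support. All sizes rest on the assumed d, the planned 350/550 split, 495 evaluable patients and an SD of 6.8 that includes the regional spread. Any improvement in the consistency probability has not been quantified and is not claimed. The point is best labelled a free improvement.

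**What to change.** Before the unblinded interim analysis:

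1. In Protocol 12.4.2 and SAP 2.5.2, add region as a fixed effect in the primary model, with two levels: Chinese, as SAP 2.2.1 defines it, and other.
2. Make the same addition to the continuous secondary models (SAP 2.6.2) and the Week 12 ANCOVA sensitivity models (SAP 2.5.4).
3. State that the term is omitted from the Chinese-only analyses, where it is constant.
4. Define Region in the SAP 2.2.1 subgroup list, so that the place of the three Taiwan sites is settled in advance.

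Randomisation can stay as it is. The cost is one degree of freedom and a few lines of wording. Country and site are already held, so no new data are needed, and if the regional difference is near zero almost nothing is lost.
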